## STUDY SUMMARY

Title	Comparison of efficacy of less invasive surfactant treatment under nasal CPAP and nasal IPPV in premature babies: CURLISPAP STUDY
Methodology	Randomized, controlled trial
Study Duration	Estimated duration for the main protocol (e.g. from start of screening to last subject processed and finishing the study) is approximately 2.0 years
Study Center(s)	Multi-center (Uludag University Hospital Marmara University Hospital, Gazi University Hospital, Ankara University Hospital Başakşehir Çam ve Sakura City Hospital and Dokuz Eylül University Hospital)
Objectives	
Primary Objective: To compare the effectiveness of nasal intermittent positive pressure ventilation (NIPPV) versus nasal continuous positive airway pressure (CPAP) in preterm infants with respiratory distress syndrome (RDS).
 
Secondary Objectives: To evaluate short and long term neonatal outcomes such as bronchopulmonary dysplasia, duration of mechanical ventilation, retinopathy of prematurity and intraventricular hemorrhage.

Number of Subjects	170 randomized patients in two arms; NCPAP and NIPPV group
Diagnosis and Main Inclusion Criteria	
Inclusion Criteria
 
 
• Gestational age 24 -29 week
 
• Clinical and radiological diagnosis of RDS
 
• Born in a hospital with a study center
 
• Spontaneous breathing
 
• Within the first 6 hours
 
• Non-invasive ventilation and FiO2 requirement >0.30
 
• Parental consent
 
 
Exclusion Criteria
 
 
• Major congenital malformations
 
• Need of mechanical ventilation
 
• Need of entubation in delivery room
 
• Air weak syndrome
 
• No parental consent
 

Study Product, Dose, Route, Regimen	
 
• NCPAP Group: Will receive standard NCPAP protocol
 
• NIPPV Group: Will receive standard NIPPV protocol
 
• SURFACTANT: As a surfactant preparation, Curosurf® will
 

	be applied in all patients with a standard dose of 200 mg / kg and a special catheter Lisacath® as a standard in all of patients.
--	---

## **PURPOSE**

To evaluate the effectiveness of nasal intermittent positive pressure ventilation (NIPPV) versus nasal continuous positive airway pressure (CPAP) in preterm infants with respiratory distress syndrome (RDS).

## **BACKGROUND**

Respiratory distress syndrome (RDS) is the leading cause of respiratory failure in preterm infants. The incidence and severity of RDS are inversely related to the gestational age of the newborn. Despite recent improvements in neonatal care, RDS still remains as major cause of morbidity and mortality in preterm infants. Exogenous surfactant treatment is known to reduce mortality and morbidity in premature infants with RDS.

Surfactant therapy should be performed by health care-givers who are experienced in intubation and MV of the newborn. Most premature infants can tolerate extubation after application of surfactant and continue with CPAP or nasal intermittent positive pressure ventilation (NIPPV) so INSURE (INTubate, SURfactant, Extubate) can be preferred as the surfactant application method. Researchers have thus been looking for less invasive ways to administer surfactant without the need for intubation. A method, called LISA (less invasive surfactant administration) in which a soft flexible catheter instead of an endotracheal tube is placed in the trachea under direct laryngoscopy using Magill forceps and the surfactant is applied. The method, non invasive ventilation (NIV) continues during the surfactant application. All meta-analyses reviewing LISA methods showed that LISA reduced the need for MV in the first 72 hours of life. LISA method can be used with NCPAP or NIPPV.

## **GOALS OF THE STUDY**

1. To compare the effectiveness of NIPPV versus NCPAP in preterm infants with RDS.
2. To evaluate the development of apnea, bradycardia, desaturation and surfactant reflux
3. To evaluate need of repeat surfactant dose
4. To evaluate need of mechanical ventilation within 72 hours following surfactant treatment
5. To evaluate duration of non invasive and invasive ventilation
6. To evaluate long term outcomes such as bronchopulmonary dysplasia, retinopathy of prematurity, intraventricular hemorrhage, necrotizing enterocolitis.

## **DURATION OF THE STUDY**

Estimated duration for the main protocol (e.g. from start of screening to last subject processed and finishing the study) is approximately 2.0 years

## **PRODUCT DESCRIPTION**

As a surfactant preparation, Curosurf® will be applied in all patients with a standard dose of 200 mg / kg and a special catheter Lisacath® as a standard.

## **STUDY ARMS**

- 1. NCPAP Group:** Will receive standard NCPAP protocol
  - a. Ventilator-derived NCPAP will be administered using binasal prongs. Standard Devices or infant flow-driver device. Initial NCPAP settings are: PEEP:6 cmH2O and FiO2: adjusted to keep preductal sPO2 between %90-94. Failure is defined as FiO2 requirement of >%50, capillary blood gas obtained at the 4th hour of therapy showing pH<7.20 or pCO2>60 cmH2O.
- 2. NIPPV Group:** Will receive standard NIPPV protocol
  - a. Ventilator-derived NIPPV will be administered using binasal prongs. Standard Devices or infant flow-driver device. Initial NIPPV settings are: PEEP:6 cmH2O, PIP: 15 cmH2O, Rate: 30-40/ bpm and FiO2: adjusted to keep preductal sPO2 between %90-94. Failure is defined as FiO2 requirement of >%50, capillary blood gas obtained at the 4th hour of therapy showing pH<7.20 or pCO2>60 cmH2O.

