### **Visit 3: (4st hours after surfactant treatment)**

- Record settings of ventilation
  - NCPAP group: PEEP, FiO2
  - NIPPV group: PIP, PEEP, FiO2 , rate, flow.
- Record blood gas analysis

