## **STATISTICAL ANALYSIS PLAN**

### **Primary Endpoint**

Need of mechanical ventilation first 72 hours in life

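### The 4th-hour pCO2 failure limit is printed in cmH2O in both arms; read literally it is 44.1 mmHg, and 60 mmHg was most likely meant

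*Combined protocol and SAP*

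**What the plan says.** The STUDY ARMS section gives each arm its starting settings and then a failure rule. The settings use cmH2O for airway pressure: "Initial NCPAP settings are: PEEP:6 cmH 2 O" in one arm and "Initial NIPPV settings are: PEEP:6 cmH 2 O, PIP: 15 cmH 2 O" in the other.

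The failure rule is worded identically in the two arms. It has an oxygen criterion, "Failure is defined as FiO 2 requirement of >%50", and a blood-gas criterion, "capillary blood gas obtained at the 4th hour of therapy showing pH<7.20 or pCO 2 >60 cmH 2 O".

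The other places that touch on blood gases add no limit and no unit. Baseline/Screening Visit 1, Visit 2 and Visit 3 (4 hours after surfactant) each carry only the instruction "Record blood gas analysis". The section on standard procedures after randomization refers to a Study Algorithm, which is not in the available text.

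The primary endpoint is "Need of mechanical ventilation first 72 hours in life". Its definition does not mention the failure rule.

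**The concern.** The unit attached to the pCO2 limit is the one the protocol uses for PEEP and PIP. It is a valid pressure unit, so the limit can be converted, but the result is far lower than the number 60 suggests to someone reading a blood gas in mmHg.

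This is the only definition of treatment failure in the text, and it is meant to be applied at six centers. A threshold of this kind should not depend on each reader silently correcting its unit. Taken at face value, it would label infants with a pCO2 in the mid-40s mmHg as failures. If failure under this rule leads to intubation, the label could reach the primary endpoint. That link is plausible, but the documents do not state it.

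**Working it through.** The limit is a stated criterion, not a derived figure, so there is no calculation of the plan's own to reproduce. The check is a unit conversion, followed by a test of which unit fits the pH limit in the same sentence.

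**Inputs from the STUDY ARMS section**
- pCO2 limit: above 60 cmH2O, both arms.
- pH limit: below 7.20, both arms.

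**Inputs that are not in the documents**
- Standard conversions: 1 cmH2O = 0.735559 mmHg; 1 mmHg = 0.133322 kPa.
- Henderson-Hasselbalch constants: pK 6.1 and CO2 solubility 0.0307 mmol/L per mmHg.
- Bicarbonate of 18 to 24 mmol/L, an assumption.

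**Step 1: the printed limit in blood-gas units**
- 60 x 0.735559 = 44.13 mmHg.
- 44.13 x 0.133322 = 5.88 kPa.

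**Step 2: comparison with 60 mmHg**
- 60 x 0.133322 = 8.00 kPa.
- In the printed unit, 60 / 0.735559 = 81.6 cmH2O.
- Gap: 60 - 44.13 = 15.87 mmHg, and 15.87 / 60 = 26.4%.

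**Step 3: which reading fits the pH limit?**

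pH = 6.1 + log10[bicarbonate / (0.0307 x pCO2)]

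Example at 60 mmHg and bicarbonate 20: 0.0307 x 60 = 1.842; 20 / 1.842 = 10.86; log10 = 1.036; pH = 7.14.

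| Assumed bicarbonate (mmol/L) | pH at 60 mmHg | pH at 44.13 mmHg |
|---|---|---|
| 18 | 7.09 | 7.22 |
| 20 | 7.14 | 7.27 |
| 22 | 7.18 | 7.31 |
| 24 | 7.21 | 7.35 |

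The range at 60 mmHg (7.09 to 7.21) includes the printed pH limit of 7.20. The range at 44.13 mmHg (7.22 to 7.35) lies wholly above it. Read literally, the pCO2 criterion would be met in infants well short of the pH criterion. Read as mmHg, the two limits describe broadly similar severity.

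**Step 4: who could be classified differently**

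Only infants with a 4th-hour pCO2 above 44.1 and up to 60 mmHg who do not already meet the pH or FiO2 criterion. The documents give no pCO2 distribution, so their number cannot be estimated.

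**The case against.** The strongest reply is that this is an editorial slip with no demonstrated consequence. To act on the literal limit, staff would have to convert a blood-gas reading into cmH2O, and nothing suggests anyone would. On that view the 26.4% measures a hypothetical misreading, not an effect on the trial. The slip is common to both arms, the sample size does not depend on it, and neither the failure rule nor the endpoint definition links the two. The Study Algorithm and the Network data-entry field, which cannot be seen here, may carry the right unit. All of this stands, and it is why the point is minor.

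The pH argument can also be challenged. It rests on an assumed bicarbonate range, its lower end at 60 mmHg (7.09) is not close to 7.20, and criteria joined by *or* need not meet at the same physiological point. That is fair: the pH comparison supports the mmHg reading but does not prove it. The main evidence is that a ventilator-pressure unit has been attached to a blood-gas value.

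None of this makes the printed unit right. An unseen algorithm might agree with the intended limit, but the protocol text would then contradict it.

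**Conclusion.** The concern holds. The pCO2 failure limit is wrong as written in both arms. Its literal value is 44.1 mmHg (5.9 kPa), which is 15.9 mmHg or 26.4% below the 60 mmHg (8.0 kPa) that was most likely intended.

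Confidence is high that the unit is an error. That conclusion needs only the printed text, and the size of the gap only a standard conversion. That mmHg was intended is an inference from the unit's use for airway pressure nearby and, with less weight, from the pH comparison under bicarbonate of 18 to 24 mmol/L.

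Severity is minor. The practical effect is probably small, the error does not by itself favour either arm, and an effect on the primary endpoint is possible but not shown.

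**What to change.** Ask the investigators to confirm the intended limit. If it is 60 mmHg, change the pCO2 criterion in both arm descriptions under STUDY ARMS to read: pCO2 >60 mmHg (8.0 kPa). Label the blood-gas field in the Network data-entry system with the same unit, and check that the Study Algorithm agrees.

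The cost is a unit correction in two places and a check of one data-entry label and one figure. No patients, visits or procedures are added.

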## **POTENTIAL BENEFITS AND RISKS TO PATIENTS**

The study includes routine treatment protocols. LISA is one of the standard surfactant treatment applications. Possible complications during surfactant treatment such as apnea, bradycardia, desaturation and surfactant reflux will be followed.

## **METHODS**

### ***Study Design.***

The prospective, multi-center, randomized, controlled study involving one hundred and seventy (170) premature with RDS.

### ***Study population and selection criteria***

Premature babies who have spontaneous breathing between 241/7 - 296/7 weeks and who have FiO2>0.3 required to reach target saturation (90-94%), who are indicated for surfactant treatment and who are within the first 6 hours of life.

***Inclusion Criteria***

- Gestational age 241/7- 296/7 week
- Clinical and radiological diagnosis of RDS
- Born in a hospital with a study center
- Spontaneous breathing
- Within the first 6 hours
- Non-invasive ventilation and FiO2 requirement >0.30
- Parental consent

***Exclusion Criteria***

- Major congenital malformations
- Need of mechanical ventilation
- Need of entubation in delivery room
- Air weak syndrome
- No parental consent

***Recruitment methods***

Subjects will be identified through of investigators in study centers. The Primary Investigators and their partners (co-investigators) will be performing the study groups treatment.

### ***Data collection and reporting***

Patient data will be collected electronically through the “Turkish Neonatal Society Trials Network” operating system. Data from the study will be maintained for two (2) years after the date the investigation is completed, terminated or until the records are no longer required to support the protocol, whichever date is later.

### ***Expected outcomes***

The study objective is to compare the effectiveness of nasal NIPPV versus CPAP in preterm infants with RDS. It is thought that the surfactant treatment by LISA with both methods will be effective.

### ***Adverse reactions***

There is no expectation of any adverse outcomes. It has been shown that surfactant administration can be performed safely with the LISA method. No risk is expected in the study, and benefits are expected in both groups.

## **REASONS FOR WITHDRAWAL OR TERMINATION**

Parents may be discontinued from the study at any time, for any reason, specified or unspecified, and without prejudice

The following is a list of possible reasons for study treatment discontinuation:

- Screening Failure
- Parents withdrawal of consent
- Lost to follow-up
- Subject death before 36 week gesatational age

## **METHODS AND STUDY SCHEDULE**

Subjects eligible for the study will review and undergo informed consent. Once consented, subjects will be randomly assigned on a 1:1 basis to undergo:

- NCPAP Group: Will receive standard NCPAP protocol
- NIPPV Group: Will receive standard NIPPV protocol

### ***Randomization***

- Patients who are hospitalized in the neonatal intensive care unit (NICU) due to RDS within the first 6 hours of life, and who are indicated for non-invasive

surfactant administration (LISA) due to their spontaneous breathing, will be randomized as **NCPAP or NIPPV**.

- Randomization will be done automatically over the Turkish Neonatal Society Trials Network system, without being user dependent.
- When entered into the system, each patient will be given a number, and each center will be able to enter their own patient's data.

### **Standard procedures after randomization**

- Patients in the NCPAP group will start CPAP with an initial pressure of 6 cm H2O, while patients in the NIPPV group will be applied 6 cm H2O pressure, 15-20 cm H2O peak inspiratory pressure, and NIPPV at a rate of 20-30 per minute.
- In both groups, the surfactant will be administered at a dose of 200 mg / kg / dose through a special catheter named Lisacath, by visualizing the vocal cords by the responsible and experienced physician in each center.
- In cases with fractional inspired oxygen FiO2 >0.3, the second dose of surfactant will be administered within the first 12 hours at least 6 hours after the first dose.
- "Study Algorithm" is presented.
- Data such as possible adverse effects, complications related to the procedure, prenatal, natal and postnatal demographic characteristics, need for repeat dose surfactant, intubation requirement and time, follow-up NCPAP / NIPPV settings will be recorded.

### **Baseline/Screening Visit 1 (-14 to -1 days from day 0)**

The following procedures will be performed at the Baseline/Screening visit:

- Review the study with the subject and obtain written informed consent
- Review and record antenatal and postnatal medical history to determine eligibility based on inclusion/exclusion criteria
- Record demographics
  - Maternal
    - Maternal age
    - Preeclampsia
    - Diabetes
    - Antenatal steroid
    - Drugs
    - Chorioamnionitis
    - Premature rupture of membranes
    - Caesarian or normal vaginal delivery
    - Multipl pregnancy
  - Neonatal

- Gestational age (week)
- Birth weight (gram)
- Apgar scores
- Gender
- Perform physical examination
- Record settings of ventilation
  - NCPAP group: Positive end expiratory pressure (PEEP), FiO2
  - NIPPV group: Peak inspiratory pressure (PIP), PEEP, FiO2 , rate, flow.
- Record blood gas analysis

### **Surfactant treatment**

- Surfactant preparation, standard Curosurf® will be applied at a dose of 200 mg / kg and a special catheter Lisacath® as standard
- Surfactant application with the LISA method, which is routinely used in the world and in our country, was well tolerated in most cases. Although sudden decreases in heart rate for less than 10 seconds can be seen in approximately half of the cases during surfactant administration by LISA method, such short-term changes in heart rate are not considered harmful for the baby. In current studies, problems such as airway damage or damage to the vocal cords have not been encountered. The treatment team will apply treatments that will reduce pain and eliminate possible discomfort when necessary.
- Surfactant reflux may occur during less invasive surfactant application.
- Surfactant reflux will be scored according to the status of reflux in the catheter, in the mouth and in the nose.

### **Visit 2: (1st hours after surfactant treatment)**

- Record settings of ventilation
  - NCPAP group: PEEP, FiO2
  - NIPPV group: PIP, PEEP, FiO2 , rate, flow.
- Record blood gas analysis

### **Visit 3: (4st hours after surfactant treatment)**

- Record settings of ventilation
  - NCPAP group: PEEP, FiO2
  - NIPPV group: PIP, PEEP, FiO2 , rate, flow.
- Record blood gas analysis

**Visit 4: (7nd days)**

- **Neonatal outcomes 1**
  - Need of mechanical ventilation and entubation, time of entubation
  - Need of repeat surfactant treatment

**Visit 5: ( Postnatal 36 gestational week))**

- Type of respiratory support
  - NCPAP
  - NIPPV
  - Mechanical ventilation
  - Head box oxygen
  - No respiratory support

**Visit 6: (discharge date)**

- **Neonatal outcomes 2**
  - Duration of total NCPAP, NIPPV, entubation and oxygen
  - Intraventricular hemorrhage
  - Bronchopulmonary dysplasia
  - Necrotizing enterocolitis
  - Retinopathy of prematurity
  - Sepsis
  - Advers events

**Unscheduled Visit**

The following procedures will be performed if the subject presents to the clinic at any other time point not specified above

- Assess for adverse events
- Assess for complications following treatments

**RANDOMIZATION**

- Patients who are hospitalized in the neonatal intensive care unit (NICU) due to RDS within the first 6 hours of life, and who are indicated for non-invasive surfactant administration (LISA) due to their spontaneous breathing, will randomized as **NCPAP or NIPPV**.
- Randomization will be done automatically over the Turkish Neonatal Society Trials Network system, without being user dependent.

- When entered into the system, each patient will be given a number, and each center will be able to enter their own patient's data.

## **SAMPLE SIZE JUSTIFICATION**

With the power analysis performed for the study, the number of samples required to determine a 15% difference in terms of going to mechanical ventilation between both groups was calculated as 170, with a power of 80% for each group. In the study, 15% of the difference in babies 26 weeks and younger; Under the assumption that the difference will be 10% for babies older than 26 weeks, it is planned to have babies aged 26 weeks and younger than 26 weeks equally in each group.

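### The sample-size sentence leaves open whether 170 is per group or in total, and with 85 per arm the stated 80% power holds only for fairly low NCPAP ventilation rates (about 22% or lower at an assumed two-sided 5%)

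*Combined protocol and SAP*

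**What the plan says.** The Sample Size Justification gives the number "required to determine a 15% difference in terms of going to mechanical ventilation between both groups" and says that it "was calculated as 170, with a power of 80% for each group". The same paragraph assumes a smaller, 10% difference in infants older than 26 weeks.

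Three other places fix how many infants each arm receives:

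- Study Summary, Number of Subjects: "170 randomized patients in two arms; NCPAP and NIPPV group".
- Methods, Study Design: a study "involving one hundred and seventy (170) premature with RDS".
- Methods and Study Schedule: "subjects will be randomly assigned on a 1:1 basis to undergo" NCPAP or NIPPV.

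Together these give 170 / 2 = 85 per arm. The primary endpoint, in the Statistical Analysis Plan, is binary: mechanical ventilation in the first 72 hours of life. The assumed NCPAP ventilation rate, the significance level, its sidedness, the test and any dropout allowance do not appear in the sample-size paragraph or elsewhere in the document.

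**The concern.** Power belongs to the comparison of two arms, not to one arm. The closing words of the sentence, "with a power of 80% for each group", therefore make little statistical sense if they qualify the power. If they qualify 170, the sentence describes a trial of 340, which is not the trial described elsewhere. The central planning figure is thus ambiguous by a factor of two.

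The ambiguity cannot be settled by recalculation, because the size of a two-proportion comparison depends on the control rate and none is given.

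This is the only power statement for the primary endpoint. If the true power is well below 80%, a non-significant result would be read as stronger evidence of similar effectiveness than it is. The Expected Outcomes section already anticipates that surfactant by LISA will be effective with both methods, which makes that misreading more likely.

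**Working it through.** **Inputs from the plan.** Difference d = 0.15, read as percentage points; power 80%; 1:1 allocation; 85 per arm.

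**Assumptions, because the plan is silent.** Two-sided alpha 5%; pooled-variance test of two proportions; no dropout; NIPPV rate p2 = p1 − 0.15, where p1 is the NCPAP rate. p1 is varied.

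**Formulas.** With p̄ = (p1 + p2)/2:

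- n per arm = [1.960·√(2p̄(1−p̄)) + 0.842·√(p1(1−p1) + p2(1−p2))]² / d²
- power = Φ{ [d·√n − 1.960·√(2p̄(1−p̄))] / √(p1(1−p1) + p2(1−p2)) }

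**Step 1: can 170 be reproduced?** Not from the plan's own inputs. It can only be matched by choosing p1.

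- *As a per-group size*, 50% v 35%: p̄ = 0.425, so √(2 × 0.425 × 0.575) = 0.699 and √(0.2500 + 0.2275) = 0.691. Then (1.960 × 0.699 + 0.842 × 0.691)² / 0.0225 = 169.3, which rounds up to 170.
- *As a total*, 22% v 7%: p̄ = 0.145, so √(2 × 0.145 × 0.855) = 0.498 and √(0.1716 + 0.0651) = 0.487. Then (1.960 × 0.498 + 0.842 × 0.487)² / 0.0225 = 85.3 per arm, about 170 in all.

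Neither match identifies what was entered. The per-group match is not unique: 65% v 50% also gives 169.3, and NCPAP rates from 46% to 69% all come close to 170 per arm, because the required size is nearly flat there (its peak is about 173).

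**Step 2: power with 85 per arm for a 15-point difference.** Example at p1 = 30%: p̄ = 0.225, d·√85 = 1.383, 1.960 × 0.591 = 1.157 and √(0.2100 + 0.1275) = 0.581. Power = Φ(0.388) = 65%.

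| NCPAP rate (assumed) | Needed per arm for 80% | Power at 85 per arm | Difference detectable with 80% power at 85 per arm |
|---|---|---|---|
| 20% | 75.1 | 85% | not calculated |
| 22% | 85.3 | 80% | about 15 points |
| 25% | 99.5 | 73% | 16.0 points |
| 30% | 120.5 | 65% | 17.5 points |
| 35% | 137.9 | 59% | not calculated |
| 40% | 151.9 | 55% | 19.6 points |
| 50% | 169.3 | 51% | 20.9 points |

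The power crosses 80% at an NCPAP rate of 21.9%.

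**Step 3: sensitivity of that threshold to the unstated choices.**

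- Continuity correction: 19.4%.
- Unpooled variance: 22.5%.
- One-sided 5%, pooled: 26.9%.
- Exact power at a rate of 22%: 81.5% for the chi-square test, 75.7% for Fisher's test.
- By symmetry the 80% is also reached at very high rates: 93% v 78% again needs 85.3 per arm.

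**Step 4: the per-group reading.** With 170 per arm (340 in total), power is 80% at 50% v 35% and never falls below about 79% at any NCPAP rate.

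**The case against.** There is a fair case on the other side.

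- *Wording.* The words about each group directly follow the power, not the number. Two explicit statements give 170 as the total, and the document has other loose phrasing. So the sentence may be only clumsily written. This stands: the wording is ambiguous, not a proven contradiction.
- *The match at 50% v 35%.* A reader might infer that the calculation gave 170 per group and that the trial therefore enrols half of what it needs. The documents do not support that. They give no control rate, the match covers a broad range of rates, and 22% v 7% fits the total reading equally well.
- *The 22% threshold.* It rests on an alpha and a test that the plan does not state. At one-sided 5%, for instance, a rate of 25% gives 83% power, not 73%. This stands too, so the threshold must be given as a range.
- *The 51% figure.* A reader might take it as the trial's actual power. It is close to the lowest value under two-sided 5% and applies only if the NCPAP rate is near 50%.

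None of this supplies the missing inputs. An NCPAP rate of about 22% or lower would rescue the 80%, but the plan would have to say so. Even at one-sided 5%, power is 76% at a rate of 30% and 63% at 50%.

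**Conclusion.** The point holds in this form: the sample-size sentence is ambiguous by a factor of two, its inputs are not stated, and with 85 per arm the stated 80% is not delivered over most of the possible range of NCPAP rates. The limit is about 22% under two-sided 5% with a pooled test, and about 19% to 27% across the variants tried, apart from the mirror case at very high rates. That a per-group number became the total is a possibility that only the sponsor's calculation can settle.

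These figures assume that every infant has the full 15-point difference and that none is lost. The plan's own second assumption, "Under the assumption that the difference will be 10% for babies older than 26 weeks", would lower power further. With equal strata, the average difference is (15 + 10)/2 = 12.5 points, and power at 85 per arm is 66% at an NCPAP rate of 20% and 48% at 30%. The conclusion here does not depend on that.

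Confidence is high that the wording is ambiguous and the inputs are missing; the true power cannot be known from the documents. The point should be corrected because the trial relies on the 80% figure.

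**What to change.** In the Sample Size Justification:

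1. Establish from the sponsor's calculation whether 170 was per group or in total, and correct the sentence to match. The wording should follow from that check, not precede it.
2. State the assumed NCPAP ventilation rate, the alpha, its sidedness and the test.
3. Restate, for the 85 per arm actually randomised, the power for a 15-point difference and the difference detectable with 80% power. Under two-sided 5% the latter would be, for example, 16 points at an NCPAP rate of 25%, 17.5 at 30% and about 21 at 50%.
4. If the calculation gave 170 per group, say so plainly beside the restated power.

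The cost is one paragraph of wording. No change in enrolment is proposed. The only downside is that the stated power may become less favourable.

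### The stated 80% power is for a 15% difference, but the plan itself expects only 10% in babies older than 26 weeks, so the trial's power for its own expected effect is lower

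*Combined protocol and SAP*

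**What the plan says.** The only power statement is in the Sample Size Justification. It gives "the number of samples required to determine a 15% difference in terms of going to mechanical ventilation" between the groups, and says this number "was calculated as 170, with a power of 80% for each group". The next sentence splits the assumed effect by gestational age. The 15% applies to babies of 26 weeks and younger; for the rest it continues "Under the assumption that the difference will be 10% for babies older than 26 weeks". It closes with "it is planned to have babies aged 26 weeks and younger than 26 weeks equally in each group".

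The Study Summary gives "170 randomized patients in two arms; NCPAP and NIPPV group", Study Design gives the same total, and Methods and Study Schedule sets 1:1 allocation. That is 170 / 2 = 85 per arm. The Inclusion Criteria admit infants up to 29 6/7 weeks, so both age groups are in the trial. The primary endpoint is "Need of mechanical ventilation first 72 hours in life", with no restriction to the younger group and no separate primary test by age.

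The section gives no control-arm rate, alpha, sidedness, test or dropout allowance.

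**The concern.** The sample size uses the effect assumed for the younger babies as if it applied to everyone, while the next sentence assumes a smaller effect in the older ones. Once any older babies are enrolled, the overall difference implied by the plan is below 15%. At a fixed size and control rate, a smaller difference means less power.

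Balancing age between the arms does not help. It prevents confounding by age but leaves the average effect unchanged. If the balancing clause means equal numbers in the two age groups, it fixes the average at 12.5.

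This is the stated power for the trial's only primary endpoint. A null result could be read as coming from a comparison with 80% power when, on the plan's own assumptions, it had clearly less.

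**Working it through.** **Inputs from the plan.** Difference 15 (26 weeks and younger) and 10 (older than 26 weeks); power 80%; 170 in total, 1:1, so n = 85 per arm.

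**Inputs assumed because the plan omits them.** Two-sided alpha 5%; differences in percentage points; no dropout; no continuity correction; control rate and age mix as shown.

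**Formula.** With control rate c, difference d, e = c − d and p̄ = (c + e)/2:

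Power = Φ( [d√n − 1.96·√(2p̄(1 − p̄))] / √(c(1 − c) + e(1 − e)) )

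**Step 1: the plan's figure.** 170 cannot be uniquely reproduced without a control rate. Solving for the rate at which 85 per arm gives 80% for 15 points yields c = 0.2194: (1.3829 − 1.96 × 0.4971)/0.4856 = 0.84, and Φ(0.84) = 80%. This choice favours the plan, since it makes the stated 80% true.

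**Step 2: the overall difference.** With share w of babies at 26 weeks or younger, d = 15w + 10(1 − w). At w = 0.50, d = 12.5.

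**Step 3: power at the same control rate, 85 per arm.**

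| Share 26 weeks or younger | Overall difference (points) | Power |
|---|---|---|
| 100% | 15 | 80% |
| 75% | 13.75 | 71% |
| 50% | 12.5 | 61% |
| 25% | 11.25 | 51% |

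For the 50% row: (1.1524 − 1.96 × 0.5144)/0.5067 = 0.28, and Φ(0.28) = 61%.

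**Step 4: other settings that also give 80% at 15 points.**

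- Control rate about 93%: 68% with equal age groups (60% to 74% for shares of 25% to 75%).
- One-sided 5%, control rate about 27%: 64% (56% to 73%).
- Differences read as relative: 85 per arm reaches 80% for a 15% reduction only near a control rate of 94.5%; a 12.5% relative reduction there has 68%.

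**Step 5: control rates that differ by age, equal age groups.**

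- Rates averaging 22%, analysed by stratum: 63% (30% younger, 14% older) and 65% (34% and 10%).
- Younger rate held at 22%, older rate lower, unstratified test:

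| Older control rate | Overall control rate | Power for 12.5 points |
|---|---|---|
| 18% | 20% | 66% |
| 15% | 18.5% | 70% |
| 13% | 17.5% | 74% |
| 11% | 16.5% | 77% |
| 10% | 16% | 79% (80% if stratified) |

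In the last row a 10-point fall leaves no older infant ventilated under NIPPV.

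**Step 6: if the calculation returned 170 per arm.** 50% versus 35% needs 170 per arm for 80%. With 85 per arm, 15 points then has (1.3829 − 1.96 × 0.6991)/0.6910 = 0.02, or 51%. Even with 170 per arm, the 12.5-point mix has 64%.

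**The case against.** - **The 80% is conditional on 15%, so no sum is wrong.** True as far as it goes: the fault is two planning statements that do not fit together. But the section goes on to say which differences it assumes, and those do not average 15. A reader will take 80% as this trial's power.
- **The plan states no overall difference and no clear age mix.** The closing clause names the younger babies in two ways and never the older ones. So 12.5 points and 61% are illustrative. The direction does not depend on them, since every mix of 15 and 10 is below 15.
- **A common control rate is implausible.** This has real force. The Background says that RDS incidence and severity fall with gestational age, and a lower rate in older babies reduces the variance. Step 5 shows 70% and 77% for older rates of 15% and 11%, and these belong beside the 61%. With 22% in the younger group, recovery to about 80% needs an older rate near 10%, and the plan gives no such rates.
- **A total of 170 also fits a control rate of about 19% with a continuity correction.** An uncorrected analysis would then have 79% (75% younger, common rate) or 81% (equal age groups, older rate 12%). That plans with one test and analyses with another. If the correction is also used in the analysis, the 81% case needs 99 per arm, so the shortfall returns.
- **The unclear phrase about each group may matter more.** It may. If 170 was meant per arm, 85 per arm was short before any mixing (Step 6). The sponsor has to settle which reading is right.

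**Conclusion.** The concern holds. The stated 80% does not apply to the effect the plan expects in the population it enrols. At a common control rate the mismatch and its direction follow from the plan's wording alone, under either reading of 170.

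The size is less certain. With 85 per arm, two-sided 5%, percentage points and a common control rate near 22%, power is about 61% for equal age groups and 51% to 71% across plausible mixes. With lower risk in older babies it is about 66% to 79% over the older rates examined (18% down to 10%). The loss all but disappears only at the extreme of that range, which nothing in the plan supports.

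**What to change.** Keep 170 in total and revise the Sample Size Justification to:

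1. state that 170 is the total, 85 per arm;
2. give the assumed control rate in each age group, the assumed age mix, whether the differences are absolute or relative, alpha, sidedness and the test;
3. replace 80% with the power of 85 per arm for the weighted difference at those inputs.

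Alternatively to item 3, state the difference detectable at 80% with 85 per arm: about 14.3 points at a 20% control rate, 17.5 at 30% and 20.9 at 50% (two-sided 5%).

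If 170 per group was intended, the Study Summary and Study Design must be reconciled with this section.

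The cost is wording, and a less favourable stated power. No extra infants are needed. For scale, holding 80% at a 22% control rate with equal age groups (22% versus 9.5%) would take about 133 per arm, 266 in total.
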